7.9.2 Pharmacodynamic Analysis

PD samples will be collected as specified in the Schedule of Trial Procedures (See Appendix D).

CCI

Additional analyses will be performed if useful and appropriate.

7.10 Other Outcomes

CCI

Additional analyses will be performed if useful and appropriate. Detailed statistical methods for biomarker will be specified in a separate biomarker analysis plan.

7.11 Safety Analysis

Safety analyses include AEs, clinical laboratory parameters, vital sign results, 12-lead ECG results, and other safety parameters. The Safety Set will be used for all summaries of safety parameters. These summaries will be presented by pooled placebo, each TAK-418 dose level, and TAK-418 overall (as appropriate). These summaries will not contain data from the fed portion. Data from the food effect cohort will be summarized separately by placebo fed, placebo fasted, TAK-418 fed, and TAK-418 fasted.

7.11.1 Adverse Events

A pretreatment event (PTE) is defined as any untoward medical occurrence in a clinical investigation subject who has signed informed consent to participate in a study, but prior to administration of any study drug; it does not necessarily have to have a causal relationship with study participation.

An AE is defined as any untoward medical occurrence in a clinical investigation subject administered a drug; it does not necessarily have to have a causal relationship with this treatment.

A TEAE is defined as any sign, symptom, syndrome, or new illness, regardless the relationship to study drug, which occurs on or after the administration of the study drug and no more than 30 days after receiving the last dose of study drug (onset data-last date of dose $+1 \le 30$). A TEAE may also be a pretreatment AE or a concurrent medical condition diagnosed prior to the date of first dose of study drug that increases in severity after the start of dosing. Any event with partially or completely missing onset date information will be considered treatment emergent unless the available information indicates that the onset occurred outside the window (onset data-last date of dose $+1 \le 30$).

All AEs will be coded by system organ class (SOC) and preferred term (PT) using the Medical Dictionary for Regulatory Activities (MedDRA, version 19 or higher).

TEAEs are recorded in the eCRF as being related or not related to study drug and study procedure. TEAEs that are recorded as related to study drug and/or study procedure will be summarized separately. TEAEs will also be presented by intensity/severity (mild, moderate, and severe). Serious TEAEs, TEAEs leading to study drug discontinuation, and TEAEs leading to death will also be summarized using SOC and PT.

When calculating the frequency and percentage of subjects who reported TEAEs, a subject will be counted only once for each SOC or PT when multiple TEAEs are coded to the same SOC or PT. For the intensity or relatedness summaries, if a subject reports multiple TEAEs coded to the same SOC or PT, the TEAE with maximum intensity or strongest relationship will be included in the summary.

AEs with missing intensity will be listed as such in the AE listings, however, will be summarized as severe in summary tables. If the relationship of an event is missing, the relationship for the event will be considered to have been related.

TEAEs will be presented by pooled placebo, each TAK-418 dose level and TAK-418 overall. The tables will include the number and percentage (N[%]) of subjects. The following summary tables will be generated:

- Overviews of TEAEs, including number of subjects and events.
- TEAEs by SOC and PT, including number of subjects and events.
- Subject mappings for TEAEs by SOC and PT.
- TEAEs by PT.

- Serious TEAEs by SOC and PT.
- Relationship of TEAEs to study drug by SOC and PT.
- Drug related TEAEs by SOC and PT.
- Drug related TEAEs by PT.
- Intensity of TEAEs by SOC and PT.
- Intensity of drug related TEAEs by SOC and PT.
- Pretreatment Adverse Events (PTE) by SOC and PT.

Data listings will be provided for PTEs, TEAEs, TEAEs leading to study drug discontinuation, SAEs, and AEs that resulted in death.

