	Screen		Predose Day 1	0	0.25	0.5	1	1.5	2	3	4	8	12	24	36	48	72	14 (±2)	91, 93, 182, 184 (±7)
PGx Evaluations												ı							1
Blood sample for DNA PGx (n)			X																
Blood sample for RNA PGx (o)			X											X					
Other			'															_	
CCI																			
Confinement			X												X				

Footnotes are on the last table page.

at the

AE=adverse event, BL-VAS=Bond-Lader Visual Analogue Scale, BMI=body mass index, C-SSRS=Columbia—Suicide Severity Rating Scale, DBP=diastolic blood pressure, ECG=electrocardiogram, ET=early termination, F-FAD=formyl-flavin adenine dinucleotide, CCI , hCG=human chorionic gonadotropin, HIV=human immunodeficiency virus, HR=heart rate, CCI , PBMC=peripheral blood mononuclear cell, PGx=pharmacogenomics, PK=pharmacokinetic, SBP=systolic blood pressure.

- (a) For Cohort 3, there will be a 7 day washout between Cohorts 3A and 3B, starting from TAK-418 administration on Day 1 for Cohort 3A. For Cohort 3B, all assessments on Days -1 through Day 4 will be same as Cohort 3A.
- (b) For all cohorts, except Cohort 3, all subjects will report back to the trial clinic to return wearable device(s) on Day 14 (±2) and will be re-evaluated per investigator's discretion. Cohort 3A subjects will return wearable devices at on Day 7 (predose Cohort 3B).
- (c) CCI

(1) **CCI** 

- (d) Predose physical and neurological examinations may be done within approximately 24 hours predose.
- (e) Vital signs and a 12-lead ECG will be performed within approximately 1 hour predose on Day 1.
- (f) CCI

  (g) CCI

  (h) CCI
- (j) A urine alcohol test may be performed at the discretion of the investigator.
- (k) Urine sample for TAK-418F concentrations may be collected at a dose level projected to produce therapeutic exposure at the following time intervals: Predose (spot collection), 0 to 12 hours, 12 to 24 hours, 24 to 48 hours.
- (n) Blood for DNA PGx will be collected within 60 minutes predose.
- (o) Blood for RNA PGx will be collected within 60 minutes predose and 24 hours postdose.
- (p) For Cohorts 1, 2, 4, and 5, CCI mandatory follow-up visit on Day 14. For Cohort 3, CCI

and returned to the site at predose Cohort 3B.

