# 11.1.6 Safety Analysis

The safety set will be used for all summaries of safety parameters. These summaries will be presented by pooled placebo, each TAK-418 dose level, and TAK-418 overall (as appropriate). Safety data collected after administration of trial drug under fed conditions will be summarized separately.

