5.0 ANALYSIS ENDPOINTS

5.1 Primary Endpoint

The primary endpoint of the study is a composite of safety variables and dose-limiting effects of TAK-418 that will be evaluated after dosing on Day 1 by the number and percentage of subjects who:

- Experience at least 1 treatment-emergent adverse event (TEAE).
- Discontinue because of an adverse event (AE).
- Meet the markedly abnormal criteria for neurological assessment measurements at least once postdose.
- Meet the markedly abnormal criteria for safety laboratory tests at least once postdose.
- Meet the markedly abnormal criteria for vital sign measurements at least once postdose.
- Meet the markedly abnormal criteria for safety 12-lead ECG parameters at least once postdose.

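### In the main TEAE tables Cohort 3 is counted over a planned 7-day fasted period beside cohorts counted to Day 14 or nominally day 30, and new AEs in men dated after the 30-day limit get no by-treatment AE count (minor)

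*SAP*

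**What the plan says.** The first item of the primary endpoint (SAP 5.1) is the number and percentage of subjects who "Experience at least 1 treatment-emergent adverse event (TEAE"). On columns, SAP 7.11.1 says "TEAEs will be presented by pooled placebo, each TAK-418 dose level and TAK-418 overall".

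**Cohort 3.** Of the main safety summaries SAP 7.11 says "These summaries will not contain data from the fed portion". Protocol 11.1.6 agrees: "Safety data collected after administration of trial drug under fed conditions will be summarized separately". A separate table shows Cohort 3 as placebo fed, placebo fasted, TAK-418 fed and TAK-418 fasted. Footnote (a) of the protocol's Schedule of Activities sets the interval: "there will be a 7 day washout between Cohorts 3A and 3B, starting from TAK-418 administration on Day 1 for Cohort 3A". Elsewhere (Protocol 6.1, SAP 4.4) 7 days is a minimum, and Protocol 6.4 lets the washout be lengthened or shortened.

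**Follow-up.** Protocol 10.2.9.1 ends routine AE collection at Day 14 (±2) in women and continues it to Day 93 and/or 184 (±7) in men.

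**TEAE limit.** SAP 7.11.1 sets it at "no more than 30 days after receiving the last dose of study drug", with the formula onset date − last dose date + 1 ≤ 30. There are two exceptions. For a condition that worsens after dosing: "A TEAE may also be a pretreatment AE or a concurrent medical condition diagnosed prior to the date of first dose of study drug". For undated events, unless the available information places onset outside the window: "Any event with partially or completely missing onset date information will be considered treatment emergent". Every AE table listed in SAP 7.11.1 is for TEAEs or pretreatment events.

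**Listings.** Protocol 11.1.6.1 puts all AEs in the listings, and SAP 7.1 lists all raw data with the study day. The listings named in SAP 7.11.1 do not include a non-serious AE that is neither pretreatment nor a TEAE.

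**The concern.** A count of subjects with at least one event depends on how long each subject is watched. Here one dose level is watched for about half as long as women in the other cohorts, and for a quarter or less of the nominal limit in men. The table shows neither the difference nor any adjustment for it. A reader could take a lower Cohort 3 count as a sign about dose. Protocol 4.2 says the safety and tolerability data will inform dose selection for a multiple-dose trial, so such a reading could carry forward.

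Separately, the protocol follows men for AEs well past day 30, but a new, dated AE in that period enters no AE table. Active and placebo cannot be compared there without counting by hand from listings.

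**Working it through.** **1. The plan's own day counts.** Protocol 1.0 gives the period of evaluation. Screening of 28 days plus the last visit day, plus 7 for Cohort 3, reproduces every figure:
- women: 28 + 14 = 42; Cohort 3: 42 + 7 = 49
- men: 28 + 93 = 121; Cohort 3: 121 + 7 = 128
- men with an abnormal Day 93 result: 28 + 184 = 212; Cohort 3: 212 + 7 = 219

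The plan itself therefore works with a 7-day fasted period.

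**2. Counting windows in the main tables.**
- Cohort 3: 7 days, taking the fed portion to start at the fed dose. The SAP has no explicit rule for assigning an AE to the fasted or fed period.
- Other cohorts, women: 14 days (12 to 16).
- Other cohorts, men: 30 days by the formula. No visit is scheduled between Day 14 and Day 91, so days 15 to 30 rest on recall or spontaneous report.

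The ratios are 14/7 = 2.0 and 30/7 = 4.3.

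**3. Mean nominal window per subject.** At least 4 of 8 subjects per cohort are men and at most 2 of those are on placebo, so at least 2 of 6 active subjects are men.
- Another dose level: (2×30 + 4×14)/6 = 19.3 days, up to 30 with six men.
- Pooled placebo (10 subjects, 2 from Cohort 3): (2×7 + 8×14)/10 = 12.6 to (2×7 + 8×30)/10 = 25.4 days.

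These are extremes of sex mix, not expected values.

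**4. Effect on counts (illustration).** The documents give no AE rate. Assume a risk P30 over 30 days, the same in all subjects, with constant hazard: p(d) = 1 − (1 − P30)^(d/30). For P30 = 30%:
- p(7) = 0.0799, or 0.479 expected subjects of six
- p(14) = 0.1533, or 0.920 of six; gap 0.44
- 10-day washout: p(10) = 0.1121, or 0.673 of six; gap 0.25
- 80% of the 14-day hazard in week one: 1 − (1 − 0.1533)^0.8 = 0.1247; gap 6 × (0.1533 − 0.1247) = 0.17
- all events in week one: gap 0

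With constant hazard, P30 = 10% gives a gap of 6 × (0.0480 − 0.0243) = 0.14, and P30 = 50% gives 6 × (0.2764 − 0.1493) = 0.76.

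**5. Chance of a misleading order, with equal true hazards.** X is the Cohort 3 count and Y that of a cohort counted to Day 14, both binomial with n = 6 and P30 = 30%.

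| Case | P(X < Y) | P(X > Y) |
|---|---|---|
| Constant hazard (0.0799 v 0.1533) | 46% | 18% |
| 80% in week one (0.1247 v 0.1533) | 38% | 27% |
| Both on 7 days (0.0799 each) | 26% | 26% |
| Both on 14 days (0.1533 each) | 33% | 33% |

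**6. Late AEs in men.** 93 − 30 = 63 of the 93 calendar days of collection lie beyond the limit. This is calendar time, not observed follow-up. Men are at least 4 × 5 = 20 of 40 subjects.

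**7. Boundary.** The SAP's words allow onset 30 days after the dose (study day 31). Its formula stops at study day 30, which is 29 days after.

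**The case against.** The strongest reply is that this follows from the design and is disclosed. Once the fed dose is given, later AEs cannot be cleanly assigned to the fasted dose. The protocol requires fed data to be kept apart, and a separate fed/fasted table exists. Listings carry the study day, so in 40 subjects any window can be counted by hand. All this is true, and it is why the planned tables should stay. But the separate table sets Cohort 3 active against Cohort 3 placebo only, and a listing is not a by-treatment count.

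A second reply is that events after a single dose tend to come early and that six subjects give noisy counts anyway. Both parts stand. The gap can be zero, and even equal 14-day windows give 33% each way.

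Three stronger readings are tempting, and the documents do not support them:
- **That men's longer window biases active against placebo within a cohort.** Treatment is randomized within cohort, so the sex mix is the same in expectation. It matters only through chance imbalance or a different sex mix between cohorts.
- **That late AEs are lost.** They are listed. A late AE that ends participation can appear as a reason in the disposition table (SAP 7.3), and a late abnormal laboratory value can enter the markedly abnormal summaries (SAP 7.11.2). Neither is an AE count. Parts of SAP 7.9.2 and 7.10 are redacted, so summaries there cannot be judged.
- **That the gap exceeds one subject of six.** At a 30% risk that needs six men fully ascertained to day 30, and no visit falls between Day 14 and Day 91.

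**Conclusion.** The point holds as a minor one about how the final tables read. By the plan's own rules, the first primary-endpoint item is not comparable between the Cohort 3 dose level and the other columns. At an assumed 30% risk over 30 days the distortion is 0 to 0.44 subjects of six against a cohort counted to Day 14. The order of counts tilts against Cohort 3 by 46% to 18% with constant hazard, or 38% to 27% with front-loading. These figures rest on an assumed AE rate, the planned 7-day interval, and the fed portion starting at the fed dose. A longer washout, or a subject who never takes the fed dose, narrows the gap.

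The absence of a by-treatment AE count after the limit rests on the text alone, and is confined to new AEs with a known onset.

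A reader might infer that dose escalation is affected. It is not: escalation uses blinded review of data after each dose (Protocol 6.2 and 11.2), not these tables.

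**What to change.** Keep the planned tables and make these additions:

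- **(a) Common-window table.** TEAE counts by dose level and pooled placebo, with onset within 7 days of the dose, or within the shortest actual fasted-to-fed interval if that is shorter, and before any second dose. State the day count explicitly.
- **(b) Late-AE table.** All post-dose AEs that fail the SAP's TEAE criterion (onset date − last dose date + 1 > 30), by pooled placebo and dose level. Note that routine collection in this period is in men only; a related SAE reported spontaneously could come from either sex.
- **(c) Wording.** Reconcile the SAP's verbal limit with its formula, which differ by one day. Word the SAP 7.11.1 listing to cover all AEs, as Protocol 11.1.6.1 does.

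The cost is two small descriptive tables and two wording changes, using data already collected. Table (a) omits later events, which stay in the planned tables.

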7.11.2 Clinical Laboratory Evaluations

Clinical laboratory tests will be assessed using the Safety Set and will be evaluated and presented using International System of Units (SI) units unless otherwise stated. Refer to Appendix D for scheduled clinical laboratory test measurements.

The central laboratory will perform laboratory tests, including hematology, urinalysis, chemistry and other tests.

For hematology, urinalysis and chemistry tests, descriptive statistics (N, mean, median, SD, minimum and maximum) will be summarized for baseline, post-baseline, and change from baseline values by treatment regimen and study visit. Only the scheduled measurements will be included in the summary.

Individual results for hematology and chemistry laboratory tests will be evaluated against the Takeda predefined laboratory markedly abnormal value (MAV) criteria (see Appendix A) using the result and criteria in SI units. All subjects with results that meet the MAV criteria will be presented in a data listing. The number and percentage of subjects with at least one post dose markedly abnormal laboratory test result will also be summarized. The mapping of the subjects who meet the MAV criteria after dosing will be listed as a table. All postdose observations, including scheduled and unscheduled measurements will be included in the MAV summaries.

Listings of all clinical safety laboratory data will be provided and will be presented in both SI and CV units. Laboratory data outside of the normal reference range will be indicated in the listings. In addition, MAVs will be flagged. The listing will include site number, subject identifier, age (at informed consent), gender, treatment group, study visit, and sample collection date.

7.11.3 Vital Signs

Descriptive statistics (N, mean, SD, median, minimum, and maximum) will be used to summarize vital sign parameters at baseline, each post-baseline visit, and change from baseline

to each post-baseline visit. Summaries will be presented by pooled placebo and each TAK-418 dose level

Individual results of vital signs that meet Takeda's markedly abnormal criteria (see Appendix B) will be summarized and provided in the data listings. If a subject has a MAV for a particular vital sign parameter, all visits for that subject for that parameter will be listed. The number and percentage of subjects with at least 1 postdose MAV signs measurement will be summarized by pooled placebo, each TAK-418 dose level and TAK-418 overall. The mapping of the subjects who meet the MAV criteria will be listed as a table. All observations, including ones at unscheduled visits, will be included in the MAV evaluation and summaries.

All vital sign results for all subjects in the Safety Set will be listed by subject in the data listings and markedly abnormal values will be flagged.

7.11.4 12-Lead ECGs

The scheduled 12-lead ECG data will be collected according to Appendix D. The ECG parameters include heart rate, PR-interval, QRS-duration, QT-interval, and QTcF interval, and the interpretation of the ECG profile by the principal investigator.

Descriptive statistics (N, mean, SD, median, minimum, and maximum) of ECG parameters will be presented for baseline, each post-baseline visit, and changes from Baseline in quantitative ECG parameters to each post-baseline visit. Only the scheduled measurements will be included in the summary. No inferential statistics will be presented.

Individual results of quantitative ECG parameters from the 12-lead safety ECGs that meet Takeda's markedly abnormal criteria (see Appendix C) will be summarized and provided in the data listings. Shift tables will be generated to show the investigator's ECG interpretations at each postdose collection by the interpretation at Baseline.

All ECG data will be presented in the listings. ECG MAVs will be flagged in the listings.

7.11.5 Other Observations Related to Safety

Physical examination findings will be presented in the data listings.

Columbia-Suicide Severity Rating Scale results will be presented in the data listings.

7.12 Interim Analysis

Not applicable.

7.13 Changes in the Statistical Analysis Plan

Not applicable.

8.0 REFERENCES

- 1. A Randomized, Double-Blind, Placebo-Controlled, Ascending Oral Single Dose Trial to Evaluate the Safety, Tolerability, and Pharmacokinetics of TAK-418 in Healthy Subjects, Takeda Development Center Americas, Inc., Amendment 01, Trial No. TAK-418-1001, dated 07 July, 2017.
- 2. **CCI**
- 3. Brian P. Simith, etc. (2000), Confidence Interval Criteria for Assessment of Dose Proportionality, Pharmaceutical Research; Vol 17, No. 10, pp 1278-1283.

Appendix A Criteria for Identification of Markedly Abnormal Laboratory Values Hematology—Criteria for Markedly Abnormal Values

Parameter	Unit	Low Abnormal	High Abnormal
Hemoglobin	Both	<0.8 × LLN	>1.2 × ULN
Hematocrit	Both	<0.8 × LLN	>1.2 × ULN
RBC count	Both	<0.8 × LLN	>1.2 × ULN
WBC count	Both	<0.5 × LLN	>1.5 × ULN
Platelet count	Conventional	$< 75 \times 10^{3} / \mu L$	$>600 \times 10^{3}/\mu L$
	SI	$<75 \times 10^{9}/L$	$>600 \times 10^9/L$

LLN=lower limit of normal, RBC=red blood cell, ULN=upper limit of normal, WBC=white blood cell.

Serum Chemistry—Criteria for Markedly Abnormal Values

Parameter	Unit	Low Abnormal	High Abnormal
Albumin	Conventional	<2.5 g/dL	
	SI	<25 g/L	
Alkaline Phosphatase	Both		>3 × ULN
ALT	Both		>3 × ULN
AST	Both		>3 × ULN
Blood urea nitrogen	Conventional		>30 mg/dL
	SI		>10.7 mmol/L
Calcium	Conventional	<7.0 mg/dL	>11.5 mg/dL
	SI	<1.75 mmol/L	>2.88 mmol/L
Carbon dioxide (Bicarbonate)	Conventional	<8.0 mEq/L	
	SI	<8.0 mmol/L	
Chloride	Both	<75 × LLN	>126 × ULN
Creatinine	Conventional		>2.0 mg/dL
	SI		>177 μmol/L
Glucose	Conventional	<50 mg/dL	>350 mg/dL
	SI	<2.8 mmol/L	>19.4 mmol/L
Gamma-glutamyl transferase	Both		>3 × ULN
Sodium	Conventional	<130 mEq/L	>150 mEq/L
	SI	<130 mmol/L	>150 mmol/L
Potassium	Conventional	<3.0 mEq/L	>6.0 mEq/L
	SI	<3.0 mmol/L	>6.0 mmol/L
Total bilirubin	Conventional		>2.0 mg/dL
	SI		>34.2 μmol/L
Total protein	Both	<0.8 × LLN	>1.2 × ULN

ALT=alanine aminotransferase, AST=aspartate aminotransferase, LLN=lower limit of normal, ULN=upper limit of normal.

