# **Chemistry**

Chemistry evaluations will consist of the following standard chemistry panel:

Albumin	Alkaline phosphatase
ALT	AST
Blood urea nitrogen	Calcium
Carbon dioxide	Chloride
Creatinine	Glucose
Gamma-glutamyl transferase	Sodium
Potassium	Bilirubin (total), if above ULN total bilirubin will be fractionated
Protein (total)	

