### 11.0 STATISTICAL METHODS

### 11.1 Statistical and Analytical Plans

A statistical analysis plan (SAP) will be prepared and finalized before unblinding of subject's treatment assignment. This document will provide further details regarding the definition of analysis variables and analysis methodology to address all trial objectives.

A targeted data review will be conducted before unblinding of subject's treatment assignment.

This review will assess the accuracy and completeness of the trial database, subject evaluability, or appropriateness of the planned statistical methods.

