Subjects in Cohort 3 will receive 2 doses (under fasted state [Cohort 3A] and fed state [Cohort 3B]), with at least 7 days washout between dose administrations. Subjects enrolled in Cohort 3A will return to the site to complete Cohort 3B and will be administered TAK-418/placebo under fed condition with a high fat/high calorie breakfast, which must be consumed within 30 minutes and the dose given within 5 minutes after the end of the meal. All assessments from Day -1 to Day 4 in Cohort 3B will be same as in Cohort 3A; however, there will be no follow-up for after Cohort 3A and the Day 14 follow-up assessment for Cohort 3B. For male subjects, days will be adjusted based on dosing in Cohort 3B.

The trial schedule is detailed in Table 4.b.

Table 4.b Trial Schedule

Screening	Pretreatment	Treat		
Period	(a)	Dose Administration (b)	Postdose Procedures (b)	Posttrial (c)
Days -28 to -2	Day -1	Day 1	Days 1 to 4	Day 14 (±2) (c)
				Days 91, 93, 182, and 184 (±7)

(a) CC

(b) Subjects will remain in the phase 1 unit for a minimum of 48 hours following the dose of trial drug and may be released after 48 hours and complete the 72 hour and later procedures at an outpatient visit. Subjects may be kept in the clinic for longer time at PI's discretion.

(c) CCI

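### SAP Appendix A prints the chloride limits as 75 × LLN and 126 × ULN: as written, every postdose chloride is flagged low, none can be flagged high, and the laboratory count in the primary endpoint is 100% in every group

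*SAP*

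**What the plan says.** The limits stand in the serum chemistry table of SAP Appendix A, titled "Criteria for Identification of Markedly Abnormal Laboratory Values". The chloride row carries the unit entry Both, a low limit of less than 75 × LLN and a high limit of more than 126 × ULN.

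SAP 7.11.2 puts the table to use. Individual hematology and chemistry results are checked against the sponsor's predefined criteria ("see Appendix A) using the result and criteria in SI units"), and subjects with at least one postdose markedly abnormal value (MAV) are counted. On which results count, it says: "All postdose observations, including scheduled and unscheduled measurements will be included in the MAV summaries".

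The count feeds the primary endpoint. SAP 5.1 lists as one component the subjects who "Meet the markedly abnormal criteria for safety laboratory tests at least once postdose"; Protocol 5.2.1 has the same component. Chloride is in the safety panel (Protocol 9.2.11.1: "Chemistry evaluations will consist of the following standard chemistry panel", with chloride in the list that follows). The schedule in SAP Appendix D places postdose chemistry at 24 hours and Day 14.

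The protocol refers to the sponsor's markedly abnormal criteria without listing limits. Appendix A is therefore the only specification in the two documents, and neither document corrects the row.

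**The concern.** A low limit of 75 times the lower limit of normal cannot be a real threshold. The nine other rows marked Both (hemoglobin, hematocrit, RBC, WBC, alkaline phosphatase, ALT, AST, GGT, total protein) use 0.5 or 0.8 on the low side and 1.2, 1.5 or 3 on the high side.

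The defect is in a threshold the analysis relies on. If it is programmed as printed, chloride alone makes every subject with a postdose sample a laboratory MAV case, on active and placebo alike. The laboratory component then carries no information, and the MAV listing and subject mapping fill with chloride entries. A truly high chloride could never be flagged. Chloride also has some relevance to this compound: Protocol 6.3.2 reports decreased plasma chloride in the 4-week rat study at 300 mg/kg/day, so the flag that loses its meaning is the one in the direction of a nonclinical finding.

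**Working it through.** The limits are specified, not derived, so there is no plan figure to reproduce. The check is to apply the printed rule and see what it flags.

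**Inputs**

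| Input | Value | Source |
|---|---|---|
| Low limit | < 75 × LLN | SAP Appendix A |
| High limit | > 126 × ULN | SAP Appendix A |
| Planned subjects | 5 cohorts × (6 active + 2 placebo) = 30 + 10 = 40 | SAP 4.4 |
| Postdose chemistry | 24 h and Day 14 | SAP Appendix D |
| LLN | 90–105 mmol/L | Assumption; the documents give none |
| ULN | 100–115 mmol/L | Assumption; the documents give none |

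**1. Limits as printed**

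- Low: 75 × 90 = 6,750; 75 × 105 = 7,875 mmol/L.
- High: 126 × 100 = 12,600; 126 × 105 = 13,230; 126 × 115 = 14,490 mmol/L.

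A check of every whole value from 50 to 200 mmol/L, over assumed ranges from 90–100 to 100–115, flagged 100% low and 0% high. The result does not depend on the assumed range: a value escapes the low flag only at 75 times LLN or more.

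**2. Subject-level count**

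P(any laboratory MAV) = 1 − (1 − p_other) × (1 − p_chloride). With p_chloride = 1 this is 1 for any p_other. As an illustration, suppose the other tests gave 0.30 on a dose level and 0.05 on placebo. The true difference would be 0.25, and the reported difference would be 1 − 1 = 0.

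If each planned subject has a postdose chloride, the counts are 6/6 at each of five dose levels, 30/30 on TAK-418 overall and 10/10 on pooled placebo.

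**3. Results affected**

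For Cohort 3, SAP 4.4 states "there will be no follow-up for after Cohort 3A", so those 8 subjects have two 24-hour samples and one Day 14 sample.

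- 32 subjects × 2 + 8 × 3 = 88 scheduled postdose results, leaving out unscheduled samples and the Cohort 3B predose sample.
- SAP 7.11 keeps fed data out of the main summaries. If the Cohort 3 Day 14 sample is assigned to the fed period, the split is 32 × 2 + 8 = 72 in the main summaries and 8 × 2 = 16 in the fed summary. The flag rate is 100% in both.

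**4. What may have been meant**

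| Reading | Low limit (mmol/L) | High limit (mmol/L) |
|---|---|---|
| Absolute limits | 75 | 126 |
| Lost decimals | 0.75 × LLN = 67.5 to 78.75 | 1.26 × ULN = 126 to 144.9 |

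Neither reading flags a chloride inside the assumed normal ranges. On the low side they differ by at most 75 − 67.5 = 7.5. On the high side the gap is 0 at ULN 100, 132.3 − 126 = 6.3 at ULN 105 and 144.9 − 126 = 18.9 at ULN 115.

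The layout does not settle the choice. All nine other Both rows are multipliers, and sodium, potassium and bicarbonate list their absolute limits on separate conventional and SI lines, which favors lost decimals. Equally, 75 and 126 are plausible as absolute limits.

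**The case against.** The strongest reply is that this is a clerical slip in one row, and that it would expose itself. A 100% flag rate on active and placebo would show at the first run. Protocol 11.1 also provides a targeted data review before unblinding that may assess the "appropriateness of the planned statistical methods". The slip may well be caught. But noticing it does not supply the right limits, and an undocumented choice between two readings would change a primary-endpoint criterion outside the signed SAP. The review is an opportunity to correct the row, not a correction.

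Second, the loss is narrower than the whole safety analysis. This stands. What fails is the subject count over all laboratory tests, together with the chloride entries in the MAV listing and mapping. MAVs for other analytes remain identifiable by test. Chloride descriptive statistics and changes from baseline are untouched, and SAP 7.11.2 also provides that "Laboratory data outside of the normal reference range will be indicated in the listings". The five other primary-endpoint components are counted separately.

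Third, no formal test uses the count, and the escalation text (Protocol 6.2 and 11.2) does not name MAV tables. Also true. The damage is to a descriptive result, but one that the plan names as part of its primary endpoint.

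Fourth, the gap between the two readings rests on assumed reference ranges and vanishes at ULN 100. That is so, but the need to confirm the row does not depend on the gap.

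Last, a fault in reading the PDF cannot be fully excluded. It is unlikely: decimals survive in neighboring rows (0.8, 1.2, 2.88, 10.7), and both chloride cells would have to be affected.

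**Conclusion.** The concern holds. As printed, the chloride row flags every postdose result low and can flag none high, for any plausible reference range. Programmed that way, the laboratory component of the primary endpoint would be 100% at each dose level and on pooled placebo among subjects with a postdose chloride, and the differences between groups would be zero by construction. The counts of 6/6 and 10/10 assume that each planned subject contributes a postdose sample. The mmol/L figures rest on assumed reference ranges, but the conclusion does not. The harm is confined to the MAV outputs and arises only if the row is applied literally. The intended limits cannot be recovered from the documents.

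**What to change.** Check the chloride row of SAP Appendix A against the sponsor's standard MAV list. Confirm two things: the form (absolute limits with units, or decimal multipliers of LLN and ULN) and the numerals. Correct the row, align the MAV program with it, and record the change as a SAP amendment or erratum before unblinding. If the correction comes out of the targeted data review, document it there and in the SAP.

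The cost is one table row and the matching line of code. No data collection or other analysis changes.
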